In Part 1, participants will receive ramucirumab 8 mg/kg followed by tusamitamab ravtansine at 170 mg/m² (150 mg/m²) at Day 1 Cycle 1, and ramucirumab 8 mg/kg followed by tusamitamab ravtansine 100 mg/m² at Cycle 2 and Q2W in all subsequent cycles. In the case that it is decided to reduce the initial loading dose of tusamitamab ravtansine to DL-1 (Table 1), a tusamitamab ravtansine loading dose of 150 mg/m² will be administered to participants on Day 1 of Cycle 1.

Table 1 - Dose levels for Part 1 (safety run-in)

[figure not shown]
Dose level (DL)	Tusamitamab ravtansine	Ramucirumab
Starting dose	170 mg/m ² Q2W Cycle 1; 100 mg/m ² Q2W Cycle 2 and thereafter	8 mg/kg Q2W
Minus -1 (DL -1)	150 mg/m ² Q2W Cycle 1; 100 mg/m ² Q2W Cycle 2 and thereafter	8 mg/kg Q2W

BSA = body surface area; DL -1=dose level -1; Q2W = every 2 weeks.

Infusion of tusamitamab ravtansine will be administered at least 1 hour after the end of ramucirumab infusion for at least the first 2 cycles. For participants with a BSA >2.2 m², the tusamitamab ravtansine dose will be calculated based on a BSA of 2.2 m².

As no overlap in the safety profiles for ramucirumab and tusamitamab ravtansine is anticipated, the starting dose for tusamitamab ravtansine is selected as the maximum tolerated dose (MTD) used in studies evaluating tusamitamab ravtansine as loading-dose monotherapy. Enough participants will be enrolled in Part 1 to achieve 6 to 12 participants evaluable for DLTs to confirm the recommended dose. The tolerability of the combination is assessed in Part 1 according to the algorithm illustrated in Figure 1. The DLT observation period is the first 2 cycles (approximately 28 days). A DLT-evaluable participant must have completed 2 cycles of treatment or have been discontinued from study treatment because of a DLT; DLT-nonevaluable participants will be replaced. A minimum delay of 1 week is required between the initial dose in the first participant treated in a DL cohort and dosing of the next 2 participants treated at the same DL.

Figure 4 Decision tree for tusamitamab ravtansine leading dose in Part 1

Note: Abbreviations: DL -1 = dose level -1 (150 mg/m²); DLT = dose-limiting toxicity.
In case of 2 or more DLTs at DL-1, an alternative dosage may be considered or the study may be stopped.

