- Formulation: CYRAMZA[®] (ramucirumab) is a concentrate for solution for infusion supplied in 10 mL or 50 mL single-use vial. Each vial contains either 100 mg ramucirumab in 10 mL (10 mg/mL) or 500 mg ramucirumab in 50 mL (10 mg/mL).
- Route of administration: IV infusion
- Dose regimen: Ramucirumab will be administered as an 8 mg/kg IV infusion administered over 1 hour on Day 1 of every 2 week cycle.

Tusamitamab ravtansine

- Formulation: tusamitamab ravtansine is supplied as a 25 mL extractable volume of concentrate for solution for infusion of 125 mg contained in a 30 mL Type I glass vial.
- Route of administration: intravenous (IV) infusion.
- Dose regimen: tusamitamab ravtansine loading dose at 170 mg/m² (or RD) will be administered via IV infusion over 1 hour 30 minutes on Day 1 of Cycle 1, followed by 100 mg/m² Q2W from Cycle 2 and in all other cycles.
- For participants with a body surface area (BSA) >2.2 m², the dose will be calculated based on a BSA of 2.2 m².

Noninvestigational medicinal products

Both tusamitamab ravtansine and ramucirumab have potential risk for IRR; therefore, premedication with an IV histamine H1 antagonist (diphenhydramine 50 mg IV or equivalent; eg, cetirizine, promethazine, dexchlorpheniramine, according to local approval and availability) given approximately at least 15 minutes before ramucirumab administration is required for all participants. If a participant previously experienced an IRR following a dose of ramucirumab or tusamitamab ravtansine, premedication for subsequent infusions will also include dexamethasone 10 mg IV and acetaminophen (paracetamol). All drugs used as premedication will be entered on the concomitant premedication page.

Posttrial access to study medication:

Not applicable.

Statistical considerations:

- **Analysis of primary endpoint:**
 - Incidence of DLTs during the DLT observation period (Cycle 1 and Cycle 2) will be summarized on the DLT-evaluable population, by DL (if applicable).

- Objective response rate (ORR) will be summarized on the all-treated population using descriptive statistics and 95% exact confidence intervals (CIs) will be provided using the Clopper-Pearson method. As a supplementary analysis, ORR will also be summarized on the activity population.
- **Analysis of secondary efficacy endpoints:**

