## Major changes in statistical analysis plan

# 1 INTRODUCTION

# 1.1 STUDY DESIGN

This is a Phase 2, open-label, multicenter, single-arm study to confirm the recommended dose, safety, efficacy (antitumor activity), and pharmacokinetics (PK) of tusamitamab ravtansine combined with ramucirumab in participants previously treated for gastric or gastroesophageal adenocarcinoma with CEACAM5-positive tumors.

The study will comprise 2 parts: Part 1 (Safety run-in) to assess the tolerability and to confirm the recommended dose (RD) of tusamitamab ravtansine in combination with ramucirumab; and Part 2, to assess the antitumor activity of tusamitamab ravtansine in combination with ramucirumab.

The screening phase will be performed only in prescreened participants determined to be CEACAM5-positive by immunohistochemistry (IHC) assessment.

Approximately 32 to 38 participants will be treated from approximately 21 sites to achieve a total of 32 participants treated at the RD and evaluable for activity.

The cycle duration is 14 days. The median expected duration of study per participant is estimated at 34 weeks (up to 4 weeks for screening, a median of 18 weeks for study intervention administration, a median of 12 weeks for end-of-treatment (EOT) assessments, and the safety follow-up visit).

Treatment allocation will be performed using interactive response technology (IRT). After being screened, eligible participants will receive tusamitamab ravtansine combined with ramucirumab until documented disease progression, unacceptable toxicity, new anticancer therapy initiation, death, or the participant's or Investigator's decision to stop the treatment.

This will be a 2-part study.

• Part 1 (safety run-in): participants will receive ramucirumab 8 mg/kg followed by tusamitamab ravtansine at 170 mg/m^2 at Day 1 Cycle 1, and ramucirumab 8 mg/kg followed by tusamitamab ravtansine 100 mg/m^2 at Cycle 2 Q2W in all subsequent cycles. In the case that it is decided to reduce the initial loading dose of tusamitamab ravtansine to Dose Level (DL)-1 (Table 1), a tusamitamab ravtansine loading dose of 150 mg/m^2 will be administered to participants at Day 1 of Cycle 1.

Dose Level (DL)	Tusamitamab revtansine	Ramucirumab
Starting dose	170 mg/m  Q2W Cycle 1;	8 mg/kg Q2W
-	100 mg/m  Q2W Cycle 2 and thereafter	
Minus -1 (DL-1)	150 mg/m  Q2W Cycle 1;	8 mg/kg Q2W
	100 mg/m  Q2W Cycle 2 and thereafter	

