#### 3.6.1.2 Tusamitamab ravtansine exposure

The dose information will be assessed by the following:

- Total number of cycles started
- Number of cycles started per participant.
- Duration of tusamitamab ravtansine exposure (in weeks) is defined by date of last administration of tusamitamab ravtansine + number of theoretical days until the next administration date of first administration of tusamitamab ravtansine/7.
- Actual dose (in mg/m^2). In case of dose interruption, actual dose will be the sum of the actual doses administered before and after the dose interruption.
- Cumulative dose (mg/m^2): the cumulative dose is the sum of all actual doses of tusamitamab ravtansine, given from first to last administration.
- Actual dose intensity (ADI in mg/m^2/week): defined as the cumulative dose divided by the duration of tusamitamab ravtansine exposure (in weeks).

- 17-Jul-2023 Version number: 1
- Planned dose intensity (PDI in mg/m^2/week): corresponds to the planned dose at C1D1 + planned dose at subsequent cycles multiplied by the theoretical total number of doses started and divided by the theoretical cycle duration expressed in weeks (ie, 2 weeks per cycle started). Note: Theoretical total number of doses started is derived based on cycles where at least one IMP is administered (even in case of dose omission), up to the end of treatment of tusamitamab ravtansine.
- Relative dose intensity (RDI, in %):  $100 \times \frac{\text{ADI}(\text{mg/m}^2/\text{week})}{\text{PDI}(\text{mg/m}^2/\text{week})}$ .

The total number of cycles started and the number of cycles started by participant will be summarized as a quantitative variable and by category (number [%] of participants receiving at least 1 cycle, at least 2 cycles, etc). Duration of tusamitamab ravtansine exposure, cumulative dose, ADI and RDI will be summarized quantitatively.

The following variables will be derived to describe dose modifications and dose interruptions:

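### The planned dose intensity formula for tusamitamab ravtansine counts Cycle 1 twice, so a fully dosed participant has a relative dose intensity below 100%

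*SAP*

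**What the plan says.** The regimen is the same in both documents. The Protocol synopsis gives "tusamitamab ravtansine at 170 mg/m² (150 mg/m²) at Day 1 Cycle 1", where the bracketed figure is the reduced dose level, and for later cycles "followed by 100 mg/m² Q2W from Cycle 2 and in all other cycles". SAP section 1.1 states "The cycle duration is 14 days".

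SAP section 3.6.1.2 builds RDI from two intensities:

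- **Actual dose intensity (ADI)** is cumulative dose divided by weeks of exposure, where "the cumulative dose is the sum of all actual doses of tusamitamab ravtansine, given from first to last administration".
- **PDI** "corresponds to the planned dose at C1D1 + planned dose at subsequent cycles multiplied by the theoretical total number of doses started", and the result is divided by the theoretical duration at 2 weeks per cycle started. A note explains the multiplier: "Theoretical total number of doses started is derived based on cycles where at least one IMP is administered", including cycles with an omitted dose, up to the end of tusamitamab ravtansine treatment.

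RDI is 100 × ADI/PDI and is summarized quantitatively. Section 3.6.1.3 uses the same multiplier and the same kind of note for ramucirumab, whose planned dose is the same at every cycle.

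**The concern.** The loading dose replaces the maintenance dose at Cycle 1; it is not given on top of it. The PDI formula adds the loading dose and then multiplies the maintenance dose by the number of all doses, so Cycle 1 is charged with both. Planned exposure is too high for every participant, and RDI is too low.

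Safety and tolerability is a secondary objective, and RDI is the summary that expresses tusamitamab ravtansine delivery as a percentage of plan. An error in its denominator would make full delivery look like underdosing. The bias shrinks as treatment lengthens, so it depends on time on treatment and cannot be removed with a single correction factor. It also creates a difference from the ramucirumab RDI that delivery does not explain.

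**Working it through.** The documents print no PDI or RDI value, so there is no figure to reproduce. The check asks whether the formula returns 100% for a participant who receives exactly the planned regimen.

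**Inputs**

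- Loading dose L = 170 mg/m², or 150 mg/m² at the reduced level (Protocol synopsis; SAP 1.1).
- Maintenance dose 100 mg/m² from Cycle 2 (same places).
- Cycle length 2 weeks (SAP 1.1).
- N = theoretical total number of doses started, Cycle 1 included (note in SAP 3.6.1.2).
- Expected median treatment duration 18 weeks (SAP 1.1), so N = 18/2 = 9 if there are no delays.

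**Formulas for full, on-time dosing**

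- Cumulative dose = L + 100(N − 1); exposure = 2N weeks.
- ADI = [L + 100(N − 1)] / 2N.
- PDI as written, with the whole sum divided by 2N = (L + 100N) / 2N.
- RDI = 100 × [L + 100(N − 1)] / (L + 100N). For L = 170 this is 100 × (70 + 100N) / (170 + 100N).

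| N | Delivered (mg/m²) | Plan as written (mg/m²) | RDI, L = 170 |
|---|---|---|---|
| 1 | 170 | 270 | 63.0% |
| 2 | 270 | 370 | 73.0% |
| 5 | 570 | 670 | 85.1% |
| 9 | 970 | 1070 | 90.7% |
| 12 | 1270 | 1370 | 92.7% |

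At N = 9, ADI is 970/18 = 53.89 and PDI is 1070/18 = 59.44 mg/m²/week. With L = 150 at N = 9, RDI is 950/1050 = 90.5%.

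**Other groupings of the same words, at N = 9 and L = 170**

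- (170 + 100) × N / 2N = 135 mg/m²/week; RDI = 53.89/135 = 39.9%.
- 170 + 100N / 2N = 220 mg/m²/week; RDI = 53.89/220 = 24.5%.

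**Ramucirumab as a check on N.** PDI = 8N / 2N = 4 mg/kg/week. Full delivery also gives 4, so RDI is 100% at every N. This works only if N includes Cycle 1, which fixes the meaning of the shared term.

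**With a real dose reduction.** Take 80 mg/m² from Cycle 3 and N = 9. Delivered dose = 170 + 100 + 7 × 80 = 830. RDI as written is 830/1070 = 77.6%; against the true plan of 970 it is 85.6%.

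**The case against.** The strongest reply is that this is loose wording whose intent is clear. The sentence separates the loading dose from later cycles, and a sensible programmer would use N − 1. The neighbouring exposure-duration definitions cannot be read strictly either. That may well be the intent, but the text says total, the note defines the total over all cycles, and the ramucirumab section needs that same definition. Literal coding gives wrong values; a silent correction leaves output that departs from the SAP. A minus sign lost in the PDF reading is not a likely explanation: where signs were lost nearby, the digit after them survived, and no stray 1 follows this phrase.

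The second reply concerns importance, and much of it stands. RDI is a descriptive exposure summary. No efficacy endpoint, DLT rule or sample size uses it; the DLT-evaluable population rests on 80% of the intended dose at each infusion. Cumulative dose, ADI, reductions, delays and omissions are reported alongside and are unaffected, so a careful reader could notice the conflict. No formal comparison of the two drugs' RDIs is planned.

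Two narrower points are also fair. The size depends on the grouping chosen, although every grouping gives less than 100%. The N = 1 figure charges a maintenance dose for a later cycle that does not exist, which is exactly what the formula does.

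**Conclusion.** The formula is wrong as written. It overstates the planned cumulative dose by 100 mg/m² for every participant under the most favourable grouping, and no other passage in either document corrects it. For full, on-time delivery with a 170 mg/m² loading dose, RDI is 73.0% at 2 cycles and 90.7% at 9, a shortfall of 9.3 percentage points at the expected median duration. The bias is always downward and is largest in participants who stop early.

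The figures assume no delays and that the whole planned sum is divided by 2N weeks. The 9-cycle example applies the 18-week median to tusamitamab ravtansine, although that median is stated for study intervention overall and one drug can be stopped before the other. The consequence is confined to the RDI summary, but it is a definite error in a prespecified, reported variable and should be corrected before the tables are produced.

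**What to change.** Replace the PDI definition in SAP section 3.6.1.2 with:

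PDI = [planned C1D1 dose + planned dose at subsequent cycles × (N − 1)] / (2 weeks × N), where N is the theoretical total number of doses started, as the note already defines it.

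The brackets remove the ambiguity about grouping. Full, on-time delivery then gives an RDI of 100% for every N and for either loading dose; at N = 9 with 170 mg/m², PDI is 970/18 = 53.89 mg/m²/week. The ramucirumab formula needs no change. The cost is one SAP definition and the matching program line. No new data are needed, and dosing and study conduct do not change.
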